**\* Recommended guidelines for use of oral diabetic agents:**

**Initiation of treatment for hyperglycemia should occur under the guidance of a pediatric endocrinologist at the local institution.** Metformin may be used per local endocrinologist's recommendations.

Other oral anti-hyperglycemic agent may be used at the discretion of the local treating institution. Insulin therapy should be directed by specialists in pediatric diabetes with the goal of normal fasting blood sugars  $< 126$  mg/dL and **HgbA1C  $< 8\%$** .

#### 6.4.3 Management of ganitumab-related infusion reactions

For patients who have allergic or acute infusion reactions, therapy modifications based on grade should be as follows. Guidelines for emergency management of infusion reactions are recommendations and institutional standard practice may be used as an alternative.

Grade	Action
Grade 1 Transient flushing or rash, drug fever $< 38^{\circ}\text{C}$ ( $< 100.4^{\circ}\text{F}$ )	
 
Slow infusion rate by 50% and monitor patient for worsening of condition. Maximum infusion duration is 120 minutes.
 

Grade 2 Rash, flushing, urticaria, dyspnea, drug fever $\geq 38^{\circ}\text{C}$ ( $\geq 100.4^{\circ}\text{F}$ )	
 
Stop infusion; symptom control (diphenhydramine hydrochloride 1 mg/kg (max 50 mg) IV, acetaminophen 10-15 mg/kg (max 650 mg) PO or IV for fever, and oxygen if needed).
 
Resume infusion at 50% of the prior rate once the reaction has decreased to <math>\leq</math> Grade 1. Monitor patient for worsening condition. Maximum infusion duration is 120 minutes.
 
For subsequent dose, premedicate with diphenhydramine hydrochloride 1 mg/kg (max 50 mg) IV.
 
If Grade 1-2 infusion reactions reoccur with subsequent dose, add dexamethasone 0.2 mg/kg (max 10 mg) IV or equivalent to premedications above. (Only dose interruption/discontinuation, but not dose reduction, is required for allergic/infusional reactions.)
 

Grade 3 Symptomatic bronchospasm with or without urticaria, allergy-related edema/angioedema, hypotension	

Stop infusion immediately.

Administer diphenhydramine hydrochloride 1 mg/kg (max: 50 mg) IV, dexamethasone 0.2 mg/kg (max: 10 mg) IV (or equivalent), bronchodilators for bronchospasms, and other medications as medically indicated. Hospital admission should be considered.

Discontinue ganitumab treatment permanently.

Grade 4 Anaphylaxis	

Stop infusion immediately

Administer diphenhydramine hydrochloride 1 mg/kg (max 50 mg) IV, dexamethasone 0.2 mg/kg (max 10 mg) IV (or equivalent), and other anaphylaxis medications as indicated. Epinephrine or bronchodilators should be administered as indicated. Hospital admission for observation may be indicated.

Discontinue ganitumab treatment permanently.

## 6.5 Dose Modifications for Hematologic Toxicity

Hematologic toxicity is considered an adverse event with the use of palbociclib and has also been reported less commonly with IGF-1R monoclonal antibodies, including ganitumab. Palbociclib dose modifications are outlined in Sections 6.5.1. Ganitumab should be held if a patient meets criteria for hematologic DLT per Section 5.4.1. For a patient's first hematologic DLT, palbociclib will be dose reduced, but ganitumab may be resumed without dose modification once the patient meets criteria to resume palbociclib according to **Table 8 or 9**. For recurrent hematologic DLTs despite one palbociclib dose reduction, ganitumab should be resumed at a lower dose according to **Table 2** in addition to any additional required dose reductions for palbociclib.

### 6.5.1 Palbociclib Dose Modifications in the Setting of Hematologic Toxicity

Patients with dose-limiting hematologic toxicity should have their palbociclib dose modified according to **Table 8 or 9** depending on whether they have bone marrow involvement by disease.

**Table 8: Palbociclib Dose Modification and Management of Hematologic Toxicities for Patients without Bone Marrow Involvement by Disease**

CTCAE Grade	Palbociclib Dose Modifications
ANC < LLN to 750/uL, or platelet count < LLN to 75,000/uL	No dose modification is required.
ANC <750 to 500/uL, or platelet count <75,000/uL to 50,000	Continue current dosing.  Dose reduction is only required if this definition of hematologic DLT is met: 
 
○ Delay in the start of subsequent cycle by > 14 days due to thrombocytopenia or neutropenia, in the absence of bone marrow disease seen on clinically-indicated bone marrow biopsy.
 

Platelet count < 50,000 to 25,000/uL	Hold palbociclib until platelet count recovers to 75,000/uL. Resume at prior dose unless one or both of these definitions of hematologic DLT is met: 
 
○ Grade 3 thrombocytopenia in association with a grade 2 or higher bleeding episode; or
 
○ Delay in the start of subsequent cycle by > 14 days due to thrombocytopenia, in the absence of bone marrow disease seen on clinically-indicated bone marrow biopsy.
 

Grade 4 neutrophil count	Suspend dose until ANC improves to $\geq$ 750 /uL.  Once recovered, resume at next lower dose (as long as neutropenia not due to progressive bone marrow involvement, in which case patient must come off protocol therapy).
Grade 4 platelet count	Suspend dose until platelet count improves to $\geq$ 75,000/uL and transfusion independent, defined as not receiving a platelet transfusion for at least 5 days prior to CBC.  Once recovered, resume at next lower dose (as long as thrombocytopenia not due to progressive bone marrow involvement, in which case patient off protocol therapy).
Patient requires administration of myeloid growth factor	Suspend palbociclib dose for at least 48 hours after the last dose of myeloid growth factor and until ANC improves to $\geq$ 750 /uL.  If growth factor was given in the setting of grade 4 neutropenia, resume palbociclib at next lower dose unless the dose was already reduced for the toxicity that led to the use of the growth factor.

**Table 9: Palbociclib Dose Modification and Management of Hematologic Toxicities for Patients Enrolling with Bone Marrow Involvement by Disease**

Hematologic criteria	Palbociclib Dose Modifications
ANC < LLN - 500/uL, or platelet count < LLN - 50,000/uL	No dose modification is required.
ANC < 500/uL, or platelet count < 50,000/uL during Cycle 1	
Continue current dosing unless:
 
 
• Life threatening infection; or
 
• Life threatening bleeding.
 
 
Dose reduction is not required unless delay in the start of subsequent cycle by > 14 days due to thrombocytopenia or neutropenia, then reduce by one dose level.

ANC < 500/uL, or platelet count < 50,000/uL during subsequent cycles	
Suspend dose until ANC improves to <math>\geq</math> 500 /uL and platelet count to <math>\geq</math> 50,000 /uL and transfusion independent, defined as not receiving a platelet transfusion for at least 5 days prior to CBC.
 
Dose reduction is not required unless delay in the start of subsequent cycle by > 14 days due to thrombocytopenia or neutropenia, then reduce by one dose level.

Patient requires administration of a myeloid growth factor	
Suspend palbociclib dose for at least 48 hours after the last dose of short-acting myeloid growth factor or 7 days after long-acting growth factor and until ANC improves to <math>\geq</math> 500 /uL.
 
Follow guidelines in preceding rows if ANC was < 500 /uL

LLN – Lower Limit of Normal

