## 5.4 Dose-Limiting Toxicity (DLT)

### 5.4.1 Definition of Dose-Limiting Toxicity

Toxicity will be graded using the CTCAE criteria, version 5. The CTCAE provides descriptive terminology and a grading scale for each adverse event listed. A copy of the CTCAE can be downloaded from the CTEP home page (<http://ctep.cancer.gov>). Any dose-limiting toxicity should be reported immediately via email to the overall Principal Investigator and to the Study Coordinator.

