#### Definition of Dose-Limiting Toxicity

DLT is defined as any of the following events that are possibly, probably or definitely attributable to palbociclib or ganitumab. A DLT may occur in any cycle and will guide dose modifications, but only DLTs occurring in the first cycle will be used for implementation of the safety monitoring rule (Section 13.4).

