#### *Non-Hematological DLT:*

- Any Grade 3 or higher non-hematological toxicity attributable to palbociclib or ganitumab with the specific exclusion of:
  - Grade 3 nausea and vomiting, anorexia, diarrhea or dehydration resolving to  $\leq$  grade 2 within 72 hours (note that grade 3 diarrhea requiring hospitalization would constitute DLT).
  - Grade 3 AST or ALT liver enzyme elevation that return to  $<$  grade 2 within 7 days (except as below if bilirubin also elevated). If grade 3 liver enzyme elevation occurs, palbociclib and ganitumab should be held and liver enzymes rechecked within 4 days of initial date of grade 3 abnormality to determine if DLT criteria have been met. See also Section 6.4.

**Recall:** For the purposes of this study the ULN for ALT is defined as 45 U/L and for AST is 30 U/L.

- Grade 3 hypophosphatemia, hypokalemia, hypocalcemia or hypomagnesemia responsive to oral supplementation within 72 hours.
- Grade 2 elevation of AST and/or ALT WITH total bilirubin  $> 2 \times$  ULN, in the absence of cholestasis.
- Any Grade 2 non-hematological toxicity that persists for  $\geq 7$  days and is considered sufficiently medically significant or sufficiently intolerable by patients that it requires treatment interruption.
- Any non-hematologic toxicity that results in delay in start of subsequent cycle by  $> 14$  days.

*Hematological DLT:*

- Hematological dose limiting toxicity is defined as:
  - Grade 4 thrombocytopenia or grade 4 neutropenia of any duration, in the absence of bone marrow disease; or
  - Grade 3 or higher febrile neutropenia with or without documentation of infection; or
  - Grade 3 thrombocytopenia in association with a grade 2 or higher bleeding episode; or
  - Delay in the start of subsequent cycle by  $> 14$  days due to thrombocytopenia or neutropenia, in patients without known bone marrow disease.

Patients with bone marrow metastatic disease at study entry will not be evaluable for hematologic DLT for the purposes of evaluating the toxicity monitoring rule. Such patients will follow the dose modification criteria in Section 6.2.1 in the setting of defined hematologic DLT.

Any Grade 5 toxicity that is possibly, probably, or definitely attributable to palbociclib or ganitumab will be considered a DLT.

Management and dose modifications associated with the above adverse events are outlined in Section 6.

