### 6.1 Dose Modification for Dose-Limiting Toxicity

Patients with protocol-defined DLT (Section 5.4.1) will have palbociclib and ganitumab held. Except where noted below for specific target toxicities, palbociclib and ganitumab will be held until resolution of toxicity to  $\leq$  Grade 1 (or baseline, whichever is higher grade), and then palbociclib and ganitumab will be resumed with dose reduction according to Sections 6.2 (palbociclib) and 6.3 (ganitumab). If a patient cannot resume therapy within 21 days of holding palbociclib and ganitumab, they will be removed from protocol therapy.

Patients with recurrent DLT (regardless of category of DLT) despite this dose reduction are eligible for up to one additional dose reduction of palbociclib. Patients with recurrent DLT despite two dose reductions of palbociclib will be removed from protocol therapy. If a second dose reduction is required for toxicity related to ganitumab, the patient will be removed from protocol therapy.

Patients who meet criteria for permanent discontinuation of one study agent (e.g., severe allergic reaction), will be removed from protocol therapy altogether rather than continuing with monotherapy.

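### Table 8 does not name febrile neutropenia, so its ANC 500-749/uL row could keep palbociclib at the current dose after an event that Sections 5.4.1, 6.1 and 6.5 treat as a DLT

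*Combined protocol and SAP*

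**What the plan says.** Section 5.4.1 lists four hematologic DLT definitions. One is "Grade 3 or higher febrile neutropenia with or without documentation of infection". A separate one is "Grade 4 thrombocytopenia or grade 4 neutropenia of any duration, in the absence of bone marrow disease". The other two are grade 3 thrombocytopenia with grade 2 or worse bleeding, and a delay of more than 14 days in the next cycle because of low counts. The section adds that "A DLT may occur in any cycle and will guide dose modifications"; only first-cycle events feed the monitoring rule in Section 13.4.

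Section 6.1 sets the general response: "Patients with protocol-defined DLT (Section 5.4.1) will have palbociclib and ganitumab held". Restart, at reduced dose, waits for recovery to grade 1 or baseline, subject to exceptions noted later for specific toxicities.

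Section 6.5 states that palbociclib is reduced at a first hematologic DLT. It also states that "Ganitumab should be held if a patient meets criteria for hematologic DLT per Section 5.4.1", and ties the ganitumab restart to meeting the palbociclib restart criteria in Table 8 or 9. It gives no matching hold sentence for palbociclib and says instead: "Palbociclib dose modifications are outlined in Sections 6.5.1".

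Section 6.5.1 directs patients with hematologic DLT and no marrow involvement to Table 8. For ANC 500-749/uL, that table continues dosing and states: "Dose reduction is only required if this definition of hematologic DLT is met". One definition follows, the delay of more than 14 days.

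**The concern.** A hematologic DLT sends the site to Table 8 for the palbociclib dose. For febrile neutropenia the table has no row, so the site would look up the neutrophil count instead. In the ANC 500-749/uL row it would find an instruction to carry on, with reduction confined to a reason that has nothing to do with fever. Sections 6.1 and 6.5 require the opposite: stop both drugs, then come back on a lower palbociclib dose.

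At stake is continued exposure to a myelosuppressive drug during febrile neutropenia, and a return to the same dose afterwards. Sites could also handle the same event differently. Neutropenia and infection are the most common grade 3 adverse events of palbociclib according to Section 2.2.2.2, so the situation is foreseeable. Ganitumab is touched as well, because its restart depends on a Table 8 criterion that does not exist for this event at ANC 500-749/uL.

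**Working it through.** The plan gives no figure to reproduce. The check sets the sections side by side for a patient without marrow involvement.

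**1. Coverage of the Section 5.4.1 definitions in Table 8**

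| Hematologic DLT (5.4.1) | Acted on in Table 8? |
|---|---|
| Grade 4 neutropenia or thrombocytopenia | Yes: suspend, then next lower dose |
| Grade 3 platelets with grade 2 or worse bleeding | Yes: named in the platelet 25,000-50,000/uL row |
| Cycle delay of more than 14 days | Yes: named in two rows |
| Grade 3 or higher febrile neutropenia | No row names it |

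Three of four definitions are acted on, and 0 of 6 rows name febrile neutropenia. The platelet row lists both its clinical trigger (bleeding) and the delay trigger. The ANC 500-749/uL row lists delay alone, so its list reads as complete.

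**2. Worked case.** An attributable grade 3 febrile neutropenia occurs at ANC 600/uL. No growth factor is given, and recovery comes early enough that the next cycle is not delayed by more than 14 days.

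- Sections 5.4.1, 6.1 and 6.5: this is a DLT; hold both drugs; reduce palbociclib.
- Table 8: carry on at the current dose; no reduction.

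The two instructions cannot both be followed.

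**3. Growth factor.** Section 5.5.2.1 allows it only for grade 3 or 4 neutropenia with documented invasive fungal infection, bacteremia, or fever with sepsis physiology. The DLT definition needs no documented infection, so some febrile neutropenia will never reach the growth-factor row. Where growth factor is given, that row does suspend palbociclib, but it requires a reduction only for grade 4 neutropenia. At ANC 500-749/uL the hold is then covered and the reduction is not.

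**4. Dependence on the ANC cut-off.** The documents do not define one, so the range is shown.

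| Assumed upper ANC limit for febrile neutropenia | Table 8 rows in conflict |
|---|---|
| below 500/uL | 0 (the grade 4 row suspends and reduces) |
| below 750/uL | 1 (the 500-749 row) |
| below 1,000/uL | 2 (also the first row, which asks for no change) |

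**5. Exposure within the cycle.** Palbociclib is given on days 1-21. Assume onset on day d with that day's dose already taken; the doses left are 21 - d.

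- d = 8: 21 - 8 = 13 doses. Cohort A 13 x 100 = 1,300 mg; Cohort B 13 x 125 = 1,625 mg.
- d = 15: 21 - 15 = 6 doses. Cohort A 6 x 100 = 600 mg; Cohort B 6 x 125 = 750 mg.

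The onset days are illustrative and the milligram figures use the starting doses. The counts are upper limits on what Table 8 would continue and Section 6.1 would hold, because the hold ends at recovery.

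**The case against.** The strongest reply is that the right action is already in the protocol. Section 6.1 holds both drugs for every DLT. Section 6.5, just above the table, says palbociclib is reduced. The sentence introducing Table 8 presupposes a modification. Section 5.4.1 also requires that "Any dose-limiting toxicity should be reported immediately via email to the overall Principal Investigator", and Section 5.2.2 blocks a new cycle until ANC is at least 750/uL. This stands. It means a site could continue dosing, not that it would. It does not remove the conflict: the table says only, and the exception clause in Section 6.1 gives a reader some ground for treating the table as the specific rule for restart and reduction. That clause does not qualify the hold.

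The second reply is that the conflict depends on febrile neutropenia occurring at ANC 500/uL or above, which the documents do not establish. This also stands. A reader might infer that listing febrile neutropenia apart from grade 4 neutropenia proves it can occur above grade 4. It does not. The grade 4 item is limited to patients without marrow disease and the febrile neutropenia item is not, so separate listing has a purpose even with a cut-off of 500/uL. What makes the assumption plausible is Section 5.5.2.1, which foresees fever with sepsis physiology at grade 3 neutropenia.

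A third reply is that setting a specific restart threshold for febrile neutropenia would be a new clinical rule. That is fair, and the fix keeps to the Section 6.1 default unless the study committee decides otherwise.

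**Conclusion.** The point holds as a conditional conflict between the dosing table and the general DLT text, for patients without marrow involvement, in either cohort and any cycle. Table 8 omits one of the four hematologic DLT definitions. If febrile neutropenia occurs at ANC 500-749/uL, the row for that range gives the wrong palbociclib action. Without growth factor, both the hold and the reduction are contradicted; with growth factor, only the reduction is left out. Below 500/uL there is no conflict.

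The conclusion rests on one assumption, that febrile neutropenia can occur at ANC 500/uL or above. How many patients this would affect cannot be derived from the documents.

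Two stronger readings are not supported. One is that the protocol has no safety rule for febrile neutropenia; Sections 6.1 and 6.5 supply one. The other is that the stopping rule is compromised. DLTs are counted from Section 5.4.1 under Section 13.4, whatever Table 8 says about dosing, so the Section 13 operating characteristics are unchanged. The matter is patient safety and consistent dose handling, and it merits correction at the next amendment.

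**What to change.** - In the ANC 500-749/uL row of Table 8, make the instruction to carry on conditional on the absence of febrile neutropenia, and add grade 3 or higher febrile neutropenia to the triggers for reduction.
- Add a Table 8 row for febrile neutropenia at any ANC, with or without growth factor, that takes precedence over the count rows. It should hold both drugs as Section 6.1 requires, then resume palbociclib one Table 1 level lower as Section 6.5 requires.
- Use the Section 6.1 default for restart (grade 1 or baseline), unless the study committee sets a specific threshold. Fever resolved with ANC at least 750/uL, the recovery level in the grade 4 neutrophil row, would be one candidate. Ganitumab then restarts on the same criterion under Section 6.5.
- Make the row apply whether or not growth factor was used, so that the growth-factor row cannot be read as waiving the reduction at grade 3 counts.

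The cost is one new row and one edited row at the next amendment. It needs no new data or visits and no change to Section 13.

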## 5.5.2 Supportive Care Guidelines

### 5.5.2.1 Use of Myeloid Growth Factors

Myeloid growth factors are only to be utilized in the setting of grade 3 or 4 neutropenia together with documented invasive fungal infection, bacteremia, or fever with sepsis physiology. The overall Principal Investigator should be notified in the event of myeloid growth factor use. Patients who receive myeloid growth factor for grade 3 neutropenia will be excluded from assessment of dose-limiting neutropenia in that cycle. If a patient receives myeloid growth factor, palbociclib and ganitumab must not be resumed until at least 48 hours following the last administered dose of short acting myeloid growth factor and until at least 7 days following the last administered dose of long-acting myeloid growth factor.

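### Table 8 sets one 48-hour minimum palbociclib hold after any growth factor, but Section 5.5.2.1 sets 7 days after a long-acting product, so patients without marrow involvement who receive one face inconsistent restart instructions

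*Combined protocol and SAP*

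**What the plan says.** Three provisions of the protocol set the time from the last growth-factor dose to restart of study drug.

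- **Section 5.5.2.1** covers every patient given a myeloid growth factor, whatever their marrow status, and both study drugs. For short-acting products, "palbociclib and ganitumab must not be resumed until at least 48 hours following the last administered dose of short acting myeloid growth factor". For long-acting products, restart is barred "until at least 7 days following the last administered dose of long-acting myeloid growth factor".
- **Table 8 in Section 6.5.1** is titled for "Management of Hematologic Toxicities for Patients without Bone Marrow Involvement by Disease". Its growth-factor row says "Suspend palbociclib dose for at least 48 hours after the last dose of myeloid growth factor" and also requires the ANC to reach 750/uL. It has no long-acting interval and does not refer to Section 5.5.2.1.
- **Table 9 in Section 6.5.1** is titled for "Management of Hematologic Toxicities for Patients Enrolling with Bone Marrow Involvement by Disease". Its hold is 48 hours "after the last dose of short-acting myeloid growth factor or 7 days after long-acting growth factor", with an ANC threshold of 500/uL.

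Two further provisions matter. Section 5.5.2.1 restricts who may receive growth factor: "Myeloid growth factors are only to be utilized in the setting of grade 3 or 4 neutropenia together with documented invasive fungal infection", with bacteremia and fever with sepsis physiology as the other qualifying conditions. Section 6.5 lets ganitumab resume after a first hematologic DLT once the Table 8 or Table 9 conditions for palbociclib are met.

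**The concern.** A site managing a patient without marrow involvement is sent to Table 8 for the palbociclib restart. If the patient received a long-acting product, a restart that complies with Table 8 can breach Section 5.5.2.1. The protocol states no order of precedence between the two. The opening of Section 6 says that delays and modifications follow the text and tables after it, which points the reader to Table 8 and not back to Section 5.

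The omission looks unintended. The eligibility washout in Section 3.1.6.5, Section 5.5.2.1 and Table 9 all separate long-acting from short-acting products. Table 8 alone does not, and no reason is given why marrow status should remove the distinction.

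At stake is consistent management of a small but seriously ill group: patients with grade 3 or 4 neutropenia and a severe infection or sepsis physiology, at the point of restarting study drug. Two sites could treat the same situation differently and both cite the protocol.

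**Working it through.** The plan gives no figure to reproduce. The check sets the passages side by side and does one subtraction.

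**Step 1. Minimum hold by product and by text.**

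| Product | Section 5.5.2.1 (all patients, both drugs) | Table 8 (no marrow involvement, palbociclib) | Table 9 (marrow involvement, palbociclib) |
|---|---|---|---|
| Short-acting | 48 hours | 48 hours and ANC at least 750/uL | 48 hours and ANC at least 500/uL |
| Long-acting | 7 days | 48 hours and ANC at least 750/uL | 7 days and ANC at least 500/uL |

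**Step 2. Which cells disagree for the same patient.** Tables 8 and 9 cover different patients, so they cannot conflict for any one person. The short-acting row agrees on time throughout. In the long-acting row, Table 9 agrees with Section 5.5.2.1 and Table 8 does not. The one operative discrepancy is Table 8 against Section 5.5.2.1, for long-acting products.

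**Step 3. Size.** 7 days is 168 hours, and 168 − 48 = 120 hours, or 5 days between the two minimum holds.

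**Step 4. When the full 5 days applies.** Table 8 also waits for the ANC. Let t be the days from the last growth-factor dose to an ANC of 750/uL, and suppose that nothing else delays restart. The earliest restart is day max(2, t) under Table 8 read alone. Section 5.5.2.1 adds that it may not be before day 7. The shortfall against Section 5.5.2.1 is max(0, 7 − max(2, t)). The values of t below are illustrative assumptions, since the documents give none.

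| t (days) | Earliest restart, Table 8 alone | Days short of Section 5.5.2.1 |
|---|---|---|
| 2 or less | day 2 | 5 |
| 4 | day 4 | 3 |
| 6 | day 6 | 1 |
| 7 or more | day 7 or later | 0 |

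Five days is therefore the largest possible shortfall, not the expected one.

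**Step 5. Ganitumab.** The Table 8 row names only palbociclib, but Section 6.5 lets ganitumab resume after a first hematologic DLT once Table 8 is satisfied. The shorter minimum can thus reach ganitumab, which Section 5.5.2.1 also holds for 7 days.

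**Step 6. How many patients.** Three conditions must all hold: growth factor was given, there is no marrow involvement, and the product was long-acting. Section 13.2 caps expected enrollment at 33. The documents give no proportion for any of the three conditions. Among patients given growth factor, the affected share could lie anywhere from 0% to 100%.

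**The case against.** The strongest reply is that both texts set minimums, so a hold that meets the longer one meets both. On this view Table 8 is an incomplete row sitting under a general prohibition, and the instructions are not mutually exclusive. There are also safeguards. Table 8 requires ANC recovery. Section 5.5.2.1 has the overall Principal Investigator notified of growth-factor use. The general DLT hold in Section 6.1 may outlast 48 hours if the accompanying infection is itself an attributable DLT.

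The logic is right and narrows the point, but it does not remove it. A reader of Table 8 alone is permitted what Section 5.5.2.1 forbids. Nothing in the table sends that reader to Section 5.5.2.1, and no rule says which text prevails. Notification allows a check on the restart but does not require one.

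A reader might also infer that restart timing distorts DLT assessment and so the toxicity objective. The documents give this little support:

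- Only first-cycle DLTs enter the monitoring rule (Section 5.4.1).
- Without marrow disease, attributable grade 4 neutropenia of any duration is already a DLT, as is attributable febrile neutropenia of grade 3 or higher. Many growth-factor recipients would have counted before any restart.
- Patients given growth factor for grade 3 neutropenia are left out of the dose-limiting neutropenia assessment for that cycle (Section 5.5.2.1).

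Restart timing could therefore rarely change a patient's neutropenia DLT status in that cycle.

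**Conclusion.** The inconsistency is real and rests on the wording alone. For a patient without marrow involvement who receives a long-acting growth factor, Table 8 and Section 5.5.2.1 give minimum palbociclib holds 5 days apart, and Section 6.5 can extend the discrepancy to ganitumab. The realized shortfall depends on neutrophil recovery and is zero once recovery takes 7 days or more.

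Two stronger readings do not hold. One is that most patients fall under conflicting rules. The documents do not give the share without marrow involvement or the expected use of long-acting products, growth factor is tightly restricted, and for short-acting products the intervals agree. The other is that Tables 8 and 9 contradict each other. They apply to different patients, and Table 9 only shows that the distinction was made elsewhere.

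This is an internal inconsistency that should be corrected. It is not a flaw in the statistical design. Which interval is right is a clinical matter and is not judged here.

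**What to change.** Reconcile the growth-factor row of Table 8 with Section 5.5.2.1 so that one restart rule applies per product type. In the same pass, check that Table 9 agrees, and that the ganitumab resumption wording in Section 6.5 leads to the same rule as Section 5.5.2.1. If the difference by marrow status is intended, say so in Section 5.5.2.1 and give the reason. A cross-reference from both tables to Section 5.5.2.1, or a sentence saying which text governs, would prevent the problem from recurring. The study team decides the interval.

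The cost is about one line in a protocol amendment and notice to the sites. Sample size, stopping boundaries and analyses do not change.
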